2.2.4 Randomisation

Randomisation will be conducted at the household level. This approach has two advantages over individual-level randomisation: (i) avoids the risk of contamination within the same household (but opens up the possibility of additive effects of multiple household members being in treatment together); (ii) reduces the risk that we alienate and / or confuse users in the control group whenever they cohabit with someone assigned to a treatment arm.

Users will enter randomisation only if/when they have completed the baseline phase. This implies that the day of randomisation is different across users even within the same households: it always happens at the end of their baseline phase (if successful), but the exact calendar day depends on when they have downloaded the app, when they have completed the onboarding, and how long it took them to complete the baseline phase (see Figure 1 for an example from a user's perspective).

The randomisation algorithm developed by HUL would then:

1. Check if another user from the same household has already been randomised

¹⁴ We consider the attrition too high if the number of users not providing their data is 10% smaller than expected at the start of the 1 month mark (see Table 6 for the expected attrition at different trial stages).

¹⁵ Results for the 5m mark will still be reported; however, we will rely on results from the 3m mark to provide an assessment of the impact of offering financial incentives.

based on their full addresses (including postcode).

- 2. If YES, the algorithm assigns this user to the same trial arm
- 3. If NO, the algorithm generates a random number from 1-100 (inclusive) for the user.
- 4. Based on the rule described in Figure 2, users are assigned to one of the 4 trial arms. Note that the control arm will be larger than the other arms. This is because at the analysis stage (5m mark), we aim at having 3 users in the control group for each user in the treatment arms. However, we expect attrition to differ across control and treatment groups, as shown in Table 6 in Section 2.4.2.4.. Based on these attrition estimates, at randomisation 12% of users will be assigned to the high incentive arm, 12% to the medium incentive arm, 15% to the low incentive arm, 61% to the control arm.

BIT's in-house IT expert will quality assure the code of the randomisation algorithm developed by HUL before the trial launch.

Figure 1. Onboarding and baseline phase from a user's point of view¹⁶.

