2.6.3.4 Overall analytical strategy

The entire analysis for this trial is based on an **intention to treat (ITT).** This means that we will assess the impact of being offered any financial incentive (compared to being offered no financial incentives).

In this trial, the unit of analysis is the individual's diet and PA outcomes repeatedly collected over multiple windows of evaluation, and the unit of randomisation is the household. To account for the clustering of observations within individuals and individuals within households, we will use linear mixed-effects models to analyse the impact of being offered any incentive (compared to being offered no incentive) for primary outcomes for both physical activity and diet.

The following table summarises the pre-specified analyses detailed in this evaluation protocol.

Table 11. Pre-specified analyses

Analyses	Research question	Outcome	Analysed	
Primary	Effect of offering financial incentive on PA	MVPA (min/day) Daily steps	Effect at 5m mark; Report	
	Effect of offering financial incentive on dietary behaviour	Fruit and vegetables (g/day) Fibre (g/day) Free sugars (% daily food energy) Saturated fat (% daily food energy)	absolute change	
Secondary	Broader effect of offering financial incentive on holistic constructs	Energy expenditure (kcal/day) Energy intake (kcal/day) Weight (kg) A healthy eating score (1-7)	Effect at 5m mark; Report absolute change	
	Short-term effects on primary outcomes (PA and diet)	MVPA (min/day) Daily steps Fruit and vegetables (g/day) Fibre (g/day) Free sugars (% daily food energy) Saturated Fat (% daily food energy)	Effect at 1m mark; Report absolute change	
	Medium-term effects on primary outcomes (PA and diet)	MVPA (min/day) Daily steps Fruit and vegetables (g/day) Fibre (g/day) Free sugars (% daily food energy) Saturated Fat (% daily food energy)	Effect at 3m mark; Report absolute change	
	Impact of different incentive levels	MVPA (min/day) Daily steps Fruit and vegetables (g/day) Fibre (g/day) Free sugars (% daily food energy) Saturated Fat (% daily food energy)	Effect at 5m mark; Report absolute change	
Expolorator y	Motivation to change behaviours	Motivation to change PA Motivation to change diet	Effect at 5m mark; Report absolute change	
	Subgroup analyses. Analysis by: deprivation level ethnic group	MVPA (min/day) Daily steps Fruit and vegetables (g/day) Fibre (g/day)	Effect at 5m mark; Report absolute	

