engagement of users with the intervention?	2.2	What are the characteristics of those who engage with the intervention for the duration of the trial, those who partly engage, and those who disengage?		engagement metrics and participant demographics (summary statistics) ii. Regression analysis of in-app engagement metrics and participant demographics

Table 14. Summar	v of research topics.	research questions	and methodologies.
	y or rooodron coproo,	1000001011 900000010110	ana mouroaologioo.

⁷¹ Moore G. F., Audrey, S., Barker, M., Bond, L., Bonell, C., Hardeman, W. et al. Process evaluation of complex interventions: Medical Research Council guidance BMJ 2015; 350 :h1258 doi:10.1136/bmj.h1258

	2.3	In what ways did users engage with the app after signing up?		Descriptive analysis of in-app engagement metrics (summary statistics)
			Qual	Thematic analysis of interviews and focus
	2.4	What were participants' experiences and perspectives of intervention?	Qual	groups with recipients and non-recipients.
	2.5	What are the barriers and facilitators to engagement with the intervention?		
Mechanisms of impact Through what mechanisms	3.1	To what extent do incentives affect in-app engagement?	Quant	Regression analysis of treatment impact on in-app engagement metrics
does the intervention affect behaviour change?	3.2	What barriers and facilitators - both contextual and individual - affect the extent to which the intervention changes behaviours for recipients and non-recipients of the financial incentives?	Qual	i. Thematic analysis of interviews and focus groups with recipients and non-recipients
	3.3 How do features of the incentive scheme affect (or not) the extent to which the scheme changes behaviours?		Qual	 ii. Thematic analysis of focus groups with delivery and reward partners
Implementatio n and feasibility How	4.1	What was the process for developing and implementing the intervention among delivery and reward partners?	Qual	Thematic analysis of focus groups with delivery and reward
was the programme implemented	4.2	Are the design and delivery processes fit for scaling and sustaining the intervention?	Qual	partners.
and is it scalable?	4.3	How was the intervention implemented?	Qual	
	4.4	What are the facilitators and barriers to scaling and sustaining the intervention (including financial incentives) beyond the pilot?	Qual	

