- baseline overweight/obesity status (BMI ≥ 25),
- ethnicity,
- deprivation status,
- disability status (self-reported presence or absence of physical or mental health conditions or illnesses lasting or expected to last 12 months or more categorised as yes, not, prefer not to say),
- education (degree or above; professional, vocational or other work-related qualifications; no qualification; prefer not to say)
- brand of wearable (Apple watch, Fitbit, Better Health fitness tracker), Garmin, others),
- study arm (control, low incentives, medium incentives, high incentives),
- baseline MVPA, and
- baseline fruit and vegetable intake.

The cut offs for each predictor will be defined following the same criteria used in the impact evaluation (unless specified above).

Estimated coefficients and statistical testing for the predictors will provide robust insights into whether overall in-app engagement differs by any demographics and baseline behaviours. The general equation for estimating the model is as below:

(4)
$$y_{ij} = \alpha + \beta Treatment_j + \gamma_X X_{ij} + u_{ij}$$

 $u_{ij} \sim N(0, \sigma_u^2)$ for all i, j

where

- y_{ij} is the proportion of weeks in the intervention period that participant *i* within household *j* is categorised as being very active;
- *Treatment* is a categorical variable for treatment group (the categories are control group, low incentives, medium incentives and high incentives, with the control group being the reference category);
- *X_{ij}* are individual level (including age, sex, ethnicity, education, disability status, baseline obesity status, baseline fruit and vegetable intake, baseline MVPA, and brand of wearable) and family level covariates (e.g. deprivation status) we will take missing values for these covariates as separate categories rather than imputing;
- u_{ij} is an idiosyncratic error term, which is assumed to follow a Normal distribution (denoted as *N*) of zero mean and a variance of σ_u^2 .

Taken together this analysis section will help to answer following questions:

- To what extent does the app reach participants?
- What are the characteristics of people taking up the programme?
- To what extent does the app engage participants?
- What characteristics predict participants' in-app engagement for the duration of the trial?
- To what extent do incentives affect in-app engagement?

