Estimated coefficients and statistical testing for the above predictors will provide robust insights into whether overall engagement with incentives differs by any demographics and baseline PA and diet behaviours. The general equation for estimating the model is similar to that of the impact evaluation:

(5)
$$y_{ij} = \alpha + \beta Treatment_j + \gamma_X X_{ij} + u_{ij}$$

 $u_{ij} \sim N(0, \sigma_u^2)$ for all i, j

where

- y_{ij} is the cumulative number of points earned (**both verified and unverified**) from randomisation to week 24 for participant *i* within household *j*;
- *Treatment* is a categorical variable for treatment group (the categories are control group, low incentives, medium incentives and high incentives, with the control group being the reference category);
- *X_{ij}* are individual level (including age, sex, ethnicity, education, disability status, baseline obesity status, baseline fruit and vegetable intake, baseline

MVPA, and brand of wearable) and family level covariates (e.g. deprivation status) - we will take missing values for these covariates as separate categories rather than imputing;

• u_{ij} is an idiosyncratic error term, which is assumed to follow a Normal distribution (denoted as *N*) of zero mean and a variance of σ_u^2 .

We will use a compound symmetry covariance structure (as is implied by the random intercepts). Linear regression will be used for continuous outcomes, and logistic regression will be used for binary outcomes.

Taken together this analysis section will help to answer following questions:

- Overall, to what extent does the intervention engage participants?
- What characteristics predict participants' engagement with the interventions?
- In what ways did users engage with specific intervention components after signing up?
- To what extent do incentives affect engagement with specific intervention components?

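### Process-evaluation regression (4) makes no provision for household clustering, and regression (5) omits the random intercept that its own text invokes

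*Protocol*

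**What the plan says.** Section 2.2.4 fixes the unit of allocation: "Randomisation will be conducted at the household level". Section 2.6.3.4 draws the consequence for the impact evaluation: "To account for the clustering of observations within individuals and individuals within households, we will use linear mixed-effects models". Equations (1) and (2) accordingly carry a household random effect.

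The quantitative process evaluation has two regressions of its own. Equation (4), section 4.2.2, models the share of weeks in which a participant counts as very active. Equation (5), section 4.2.3, models cumulative points earned. Both index participant i in household j and include Treatment_j and covariates. In both, the only random term is u_ij, which "is an idiosyncratic error term, which is assumed to follow a Normal distribution" with constant variance.

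Section 4.2.2 says nothing further about dependence between household members. Section 4.2.3 introduces (5) with "The general equation for estimating the model is similar to that of the impact evaluation" and adds after it: "We will use a compound symmetry covariance structure (as is implied by the random intercepts".

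Both regressions are meant for inference. For (4) the protocol states: "Estimated coefficients and statistical testing for the predictors will provide robust insights into whether overall in-app engagement differs". Table 14 lists, for the question whether incentives affect engagement, "Regression analysis of treatment impact on in-app engagement metrics".

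**The concern.** Study arm is constant within a household, so its coefficients are between-household contrasts. A model with independent errors counts two co-resident adults as two independent pieces of evidence about the arm. If their engagement is positively correlated, the arm standard errors and p-values come out too small. The same applies to covariates shared by a household, such as deprivation.

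The protocol accepts this argument for its impact models and expects correlated outcomes within households (Appendix B). It gives no reason for leaving the household term out here. This is also not a detail visibly left for later: the models are written out in full, and section 4.2 describes the text as the final quantitative process evaluation.

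At stake is the reliability of the tests of whether incentives raise app use and points earned. For (5) there is a further problem: two analysts could fit different models and each cite the protocol.

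**Working it through.** **1. The equations side by side.** Equation (2) contains a household effect with its own distribution line. Equations (4) and (5) have no such term, no distribution line for one and no definition of one. Each participant contributes a single value to (5). Any random intercept there can therefore only sensibly be at household level; the protocol makes the same remark about person-level effects under (2). So the sentence after (5) describes a household term that the equation lacks. Section 4.2.2 has no corresponding sentence for (4).

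**2. Inputs.** Households with 1, 2 and 3 adults: 39%, 41%, 20%, all adults signing up (Table 5). ICC 0.3 and pre-post correlation 0.5 (section 2.4.2.2). ICC range 0.2 to 0.5, with 0.2 to 0.4 called more realistic (Table 5). These ICCs are for physical activity and diet; none is given for engagement.

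**3. Check of these inputs against the plan's own figures.** Mean size = 0.39×1 + 0.41×2 + 0.20×3 = 1.81, and 4,200/1.81 = 2,320 households (stated: about 2,300). With design effect 1 + (1.81 − 1)×0.3 = 1.243, a two-sided 5% level (assumed, as it is not stated) and Bonferroni division by 4:

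MDES = 190 × √(1 − 0.5²) × √1.243 × (2.498 + 0.842) × √(2/2,100) = 18.9 g/day for fruit and vegetables (stated: 18.7).

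The other five agree within 3%: MVPA 2.39 (2.4), steps 376 (371), fibre 0.746 (0.74), free sugars 0.627 (0.63), saturated fat 0.318 (0.31). Without clustering the first figure would be 16.96, so the plan's power calculation did allow for clustering.

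**4. Effect on an arm coefficient.** Design effect DE = 1 + (m − 1)×ICC; naive/correct SE = 1/√DE; actual size of a nominal 5% test = 2×(1 − Φ(1.96/√DE)). Two values of m are shown because Table 25 gives 39/41/20 as shares of households, while the worked example in Appendix B applies them to participants. As participant shares, m = 1.81. As household shares, the size-weighted mean is (0.39×1 + 0.41×4 + 0.20×9)/1.81 = 3.83/1.81 = 2.116.

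| ICC | DE (m = 1.81 / 2.116) | Naive/correct SE | Actual size of 5% test |
|---|---|---|---|
| 0.07 | 1.057 / 1.078 | 0.973 / 0.963 | 5.66% / 5.91% |
| 0.2 | 1.162 / 1.223 | 0.928 / 0.904 | 6.90% / 7.64% |
| 0.3 | 1.243 / 1.335 | 0.897 / 0.866 | 7.88% / 8.98% |
| 0.4 | 1.324 / 1.446 | 0.869 / 0.831 | 8.85% / 10.32% |
| 0.5 | 1.405 / 1.558 | 0.844 / 0.801 | 9.82% / 11.64% |

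The 0.07 row is the lowest ICC that Appendix B cites (accelerometer MVPA in families with children).

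**5. Simulation.** Ordinary least squares on about 15,500 users in households of 1 to 3 adults (39/41/20 as household shares), allocated 61/15/12/12% by household, no true effects, 1,500 runs, ICC 0.3:

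| Coefficient | Naive SE / empirical SD | Rejection, naive | Rejection, cluster-robust |
|---|---|---|---|
| High-incentive arm | 0.85 | 10.6% | 5.8% |
| Deprivation (household level) | 0.86 | 9.7% | 5.6% |
| Sex (opposite in couples) | 1.13 | 2.5% | 4.5% |

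The Monte Carlo standard error near 9% is √(0.09×0.91/1,500) = 0.7 points, so 10.6% lies about two standard errors above the analytic 8.98%. Over ICCs of 0.2, 0.3 and 0.5 the cluster-robust rejection rates were 4.2 to 5.8%.

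**The case against.** A reader might infer that the p-values of both regressions are shown to be too small throughout. The documents do not support that, for two reasons.

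- For (5), the text announces compound symmetry from random intercepts and a model like that of the impact evaluation. An analyst who follows the text handles the clustering. The later sentence assigning linear or logistic regression by outcome type does not exclude random intercepts, since section 2.6.3.5 itself calls the mixed model a panel regression with random effects. What is shown for (5) is a contradiction, not wrong standard errors.
- Many predictors in (4), such as age, sex, education and device brand, belong to individuals. For one that varies within households the error can reverse, as the sex row shows.

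The size is also uncertain. Sign-up by every adult is the protocol's declared conservative case, section 2.5.1 does not require it, and a footnote in Appendix B suggests that households in the trial may be smaller. Fewer co-enrolled adults would shrink the effect.

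Finally, the arm differences may be too large for this to matter. Taking Table 6 attrition as a rough proxy for engagement, control against low incentive (78% v 69%; 9,400 and 2,250 users) gives z = 0.09/√(0.78×0.22/9,400 + 0.69×0.31/2,250) ≈ 8.5. Control against high (78% v 62%; 9,400 and 1,900) gives about 13.4 in the same way. Dividing by √1.335 leaves about 7.3 and 11.6.

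All of this limits the consequence, and the last point may well hold for arm against control. It does not cover smaller contrasts or the deprivation coefficient, and it does not make (4) a correct specification for a household-randomised trial.

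**Conclusion.** Equation (4) is wrong as written: it makes no provision for clustering although arms are allocated by household. Equation (5) contradicts its own text and cannot be implemented without guessing which of the two governs.

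For arm and household-level coefficients under independent errors, the approximate upper range at ICC 0.3 is standard errors 10 to 13% too small and a nominal 5% test at about 8 to 9%; over ICC 0.2 to 0.4 the test runs at about 7 to 10%. This rests on three assumptions: positive within-household correlation in engagement, of the size the protocol gives for activity and diet; sign-up by all adults in a household; and a two-sided 5% level.

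The effect is moderate and confined to the process-evaluation regressions. The primary and secondary impact models already carry the household effect.

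**What to change.** Add the household random intercept of equation (2), with its distribution line and definition, to equations (4) and (5). Alternatively, state for both that standard errors will be cluster-robust by household. Then make the covariance sentence in section 4.2.3 match the chosen form, and put the same statement in section 4.2.2.

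The cost is one term, or one sentence, in two places. No new data are needed: Table 10 already lists household ID as a mandatory field collected for analysis.

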4.2.4. Analysis of 'gaming' and data errors

The final section of the quantitative IPE will involve a descriptive analysis of 'gaming' and data errors. Table 18 summarises the metrics that will be used to conduct this analysis. These metrics will be operationalised and collected from HUL and our analyses rely on HUL sharing these metrics.

Metric	Data source	Number of timepoints	Number of groups	Which groups
% of consenting participants with unreasonable body measurements (e.g. BMI over 100 kg/m2) at any timepoint from randomisation to week 24 (in %)	In-app survey	1 (total timespan)	5	Total and by study arm
% of non-validated points earned by study arm from randomisation to week 24 (in %)	In-app data	1 (total timespan)	5	Total and by study arm
% of non-validated points earned by study arm, per month from randomisation to week 24 (in %)	In-app data	5 (monthly)	5	Total and by study arm
Subgroup analysis on the % of non-validated points earned by study arm from randomisation to week 24	In-app data	1 (total timespan)	80	Total and by study arm. Each respectively by deprivation status, ethnicity, sex, age, baseline F&V intake, baseline MVPA.

Table 18. Metrics underlying the	'potential gaming and data errors' analysis.
rable re: meaned and mying are	potoritial garning and data orroro analysis.

Summary statistics will be calculated using data on the above metrics for the entire participant sample and by study arm. Additionally we will conduct subgroup analyses on the % of non-validated points earned by study arm from randomisation to week 24 to understand if potential gaming and data error varies by deprivation status, ethnicity, sex, age, baseline F&V intake, baseline MVPA. This section of the quantitative IPE will help to quantify the extent of 'gaming' and data errors in the intervention.

4.3 Qualitative Methods

4.3.1 Methods overview

The qualitative component of the IPE will provide rich evidence of individuals' perspectives and experiences of the intervention's implementation to complement the broad insights obtained through quantitative methods.

BIT has identified five target populations who can provide partial perspectives on intervention experience and these will be combined for a comprehensive interrogation of the research questions:

- **"Fully engaged" recipients**: people who have accessed the app at least once every 30 days for the duration of the trial.
- "Drop out" recipients: people who signed up to the intervention but have not used the app for more than 30 days consecutively.
- **Non-recipients**: people who were targeted by HUL, but chose not to participate in the intervention. This consequently excludes individuals who were on the waiting list to join the intervention.
- **Delivery partner**: employees of HUL who have been involved in the design and delivery of the intervention.
- **Reward partners**: employees from both corporate and local partners who have been involved in the design and delivery of the incentives to recipients.
- **City of Wolverhampton Council (CWC):** members of staff at WCW both in leadership positions and frontline positions to understand their experiences of supporting the implementation of the scheme.

We will use purposive sampling to capture the views of a diverse range of people from the target populations listed above. Selecting participants based on particular characteristics (see sampling frames in Section 4.3.2.1 for more detail) will ensure that the full range of relevant groups are included in the data collection. This enables us to capture a diverse set of perspectives and experiences.

For each population, BIT has selected a qualitative methodology that will best enable the IPE research questions to be addressed (see Section 4.3.2.3 for detail on methodologies). Namely, BIT will conduct: (i) interviews and focus groups with recipients (fully-engaged and drop-outs) and non-recipients of the intervention; (ii) focus groups with the delivery partner (HUL); and, (iii) focus groups with reward

partners. The key research questions the qualitative component of the IPE will focus on are:

Table 10	Research	tonics	and	nuestions
	Research	lopics	anu d	Juesuons

Research Topic	Resea	arch question
Reach What factors affected the intervention's	1.4	What was the role of marketing and communications in motivating participants to join the intervention?
reach?	1.5	How is the intervention perceived by recipients, and non-recipients of the financial incentives?
	1.6	What are the barriers and facilitators to the intervention's reach?
Engagement What factors affected the engagement of	2.3	In what ways did users engage with the app after signing up?
users with the intervention?	2.4	What were participants' experiences and perspectives of the intervention?
	2.5	What are the barriers and facilitators to engagement?
Mechanisms of impact Through what mechanisms does the	3.2	What barriers and facilitators - both contextual and individual - affect the extent to which the intervention changes behaviours for recipients and non-recipients of the financial incentives?
intervention affect behaviour change?	3.3	How do features of the incentive scheme affect (or not) the extent to which the intervention changes behaviours?
Implementation and feasibility4.1How was the4.1		What was the process for developing and implementing the intervention among delivery and reward partners?
intervention implemented and is it scalable?	4.2	Are the design and delivery processes fit for scaling and sustaining the intervention?
	4.3	How was the intervention implemented?
	4.4	What are the facilitators and barriers to scaling and sustaining the intervention (including financial incentives) beyond the pilot?

Our approach to conducting this fieldwork will be underpinned by three qualitative strategies: triangulation to assess the qualitative research findings' credibility,⁷⁷

⁷⁷Patton M. Q. (1999). Enhancing the quality and credibility of qualitative analysis. Health services research, 34(5 Pt 2), 1189–1208. Triangulation is a strategy to assess qualitative findings' credibility by enabling "cross-data validity checks". Two forms of triangulation will be employed in this study. Methodological triangulation will be used to establish the findings' validity by testing conclusions across different methods. This will be achieved both through the combination of qualitative and quantitative research and the use of different qualitative techniques (i.e., focus groups and interviews). For example, the quantitative IPE will help us understand "what" happened, whilst the qualitative IPE will help answer "why". Triangulation of sources will build a richer picture of the pilot's implementation by combining data from different users (e.g., recipients of the intervention, reward partners and implementation partners).

ongoing assessment of thematic saturation⁷⁸ to guide fieldwork priorities and the use of the Theoretical Domains Framework⁷⁹ (TDF) to ensure a comprehensive assessment of factors affecting the intervention's implementation. Anonymous quotations or written summaries of participants' responses may be included in the final report, presentation or other deliverables. However, all identifiable information including, names, roles etc - will be removed.

Once data collection is complete, BIT will use thematic analysis across the qualitative data to detect themes, patterns and key ideas (see Section 4.4 for more details). We will take an inductive, data-driven approach to analyse patterns and develop themes closely linked to the data. This will be complemented by a contextualist method that takes into account the individual perspective, as well as the social context into account, while maintaining focus on the data collected. Table 20 provides an overview of the data sources, collection methods and analysis strategy BIT will undertake to answer the key research topics for each population .

Research topic	Data collection methods		Data sources	Data analysis methods
 Reach Engagement Mechanisms of impact Implementation and feasibility 	Intervention Recipients / Non-recipients	34 Semi-structured interviews	 12 x Fully engaged intervention recipients 12 x Dropout intervention recipients 10 x Intervention non-recipients 	Thematic analysis
		3 Focus groups	 1 x Fully engaged intervention recipients (4 participants - 1 per arm) 1 x Dropout intervention recipients (4 participants - 1 per arm) 1 x Intervention non-recipients (4 participants) 	Thematic analysis
4.Implementation and feasibility	Delivery partner	2 x focus groups	2 x focus groups (2-5 participants per focus group)	Thematic analysis
4.Implementation and feasibility	Reward partners	3 x focus groups	2 x focus group with national supermarket	Thematic analysis

Table 20. Summary of Qualitative IPE research activities

⁷⁸ Green, J., & Thorogood, N. (2004) Qualitative methods for health research (2nd ed., pp. 198-202). London: Sage Publications. Qualitative findings are not intended to be objective or statistically generalisable. Rather, they aim to uncover the meaning of people's behaviour as defined by themselves. Thematic saturation is achieved when further data collection or analysis do not surface new information to elucidate the research questions. Periodic assessment of saturation at the group level to assess whether no new themes are emerging in new interviews). This will allow BIT to strategically target our qualitative research to address thematic gaps.

⁷⁹ Michie, S., Johnston, et al., & "Psychological Theory" Group (2005). Making psychological theory useful for implementing evidence based practice: a consensus approach. Quality & safety in health care, 14(1), 26–33. The TDF identifies twelve domains that explain behaviour change (e.g., knowledge, skill and beliefs about capabilities). Understanding the role of these domains in behaviour change can provide a more comprehensive understanding of the factors that may serve as a barrier or facilitation to a behaviour. The TDF ensure that the interview and topic guides fully address all factors contributing to reach (e.g., social influences of peers on sign-up), engagement (e.g., the extent to which rewards successfully reinforce intentions) and mechanisms of success (e.g., people's belief in their ability to lose weight).

			(2-3 participants per focus group) 1 x national gyms 2-3 participants per focus group)	
1. Reach 4. Implementation and feasibility	City of Wolverhampton Council	2 x focus groups	2 x focus group with Local Authority (4-5 participants per focus group)	Thematic analysis

Fully engaged intervention recipients* are recipients **who remained engaged throughout the pilot and did not drop-out. These interviews and the focus group will be conducted at the end of the pilot.

Since each population has a slightly different journey through the research process, the sections below outline the sampling frame, recruitment strategy and data collection methods for each population (i.e., (i) recipients and non-recipients, (ii) delivery partner and (iii) reward partners) separately.

